## Protocol Synopsis

### ANTEGRADE-PVD Post-Market Registry Protocol

**A MULTI-CENTER, PROSPECTIVE, POST-MARKET REGISTRY TO EVALUATE PROCEDURAL OUTCOMES DATA USING THE CARDIVA VASCADE™ VASCULAR CLOSURE SYSTEM (VCS) FOR THE MANAGEMENT OF THE FEMORAL ARTERIOTOMY AFTER PERCUTANEOUS ENDOVASCULAR PROCEDURES VIA ANTEGRADE ACCESS**

Primary Objective	
The objective of the ANTEGRADE-PVD registry is to collect procedural outcomes data when the Cardiva VASCADE™ Vascular Closure System (VCS) is used to seal femoral arterial access sites at the completion of ipsilateral peripheral interventional procedures performed through 5-7 Fr introducer sheaths via an antegrade approach.
 
Antegrade access is experiencing growing adoption in catheter-based procedures to treat peripheral artery disease, with many advantages for lower limb procedures in particular. This post-market registry is designed to capture data specific to this procedural technique, and is being conducted under an FDA-approved indication for use for this device.

Device	The Cardiva VASCADE™ Vascular Closure System (VCS) is an FDA-approved device (PMA P120016).
Approved Indication for Use	The Cardiva VASCADE™ Vascular Closure System (VCS) is indicated for femoral arterial access site closure while reducing times to hemostasis and ambulation in patients who have undergone diagnostic or interventional endovascular catheterization procedures utilizing a 5 Fr, 6 Fr or 7 Fr procedural sheath.
Study Design	A multi-center, prospective, single arm post-market registry
Number of Subjects	Up to 100 prospectively enrolled subjects
Number of Sites	Investigators experienced in antegrade access closure w/VASCADE VCS will enroll subjects at up to 7 U.S. sites
Study Duration	It is anticipated that enrollment will commence in December 2016, with final enrollment and 30 day follow-ups completed in Q3 2017. The registry will be considered complete after all enrolled subjects have completed the registry follow-up requirements.

Follow-up Schedule	Each enrolled subject will be followed for up to 30 +/-7 days post-procedure. There will be an office visit between 1-15 days; and a subsequent telephone follow-up will be done between 23-37 days as the final contact.
Primary Procedural Outcome – Performance	
 
• Time to hemostasis (TTH), defined as elapsed time between device removal and first observed and confirmed arterial hemostasis.
 

Secondary Procedural Outcomes - Performance	
 
• Time to ambulation (TTA), defined as elapsed time between device removal and when subject first stands and walks 20 feet without evidence of arterial re-bleeding from the access site.
 
• Time to hospital discharge (TTD), defined as elapsed time between device removal and when subject is actually discharged from the facility.
 
• Device Success, defined as the ability to deploy the delivery system, deliver the collagen, and achieve hemostasis with the Cardiva VASCADE™ VCS alone or with adjunctive compression
 
• Procedure Success, defined as attainment of Device Success and freedom from major access site closure-related complications through 30 days
 

Primary Procedural Outcomes - Complications	
Patient incidence rate of combined major access site closure-related complications through 30 days:
 
 
• Access site closure-related bleeding requiring transfusion;
 
• Vascular injury requiring repair (via surgery, ultrasound guided compression, transcatheter embolization or stent graft);
 
• New ipsilateral lower extremity ischemia causing a threat to the viability of the limb and requiring surgical or additional percutaneous intervention;
 
• Access site-related infection requiring intravenous antibiotics and/or extended hospitalization;
 
• New onset neuropathy in the ipsilateral lower extremity requiring surgical repair
 
• New onset permanent nerve injury in the ipsilateral lower extremity (> 30 days)
 


Secondary Procedural Outcomes - Complications
	
Patient incidence rate of combined minor access site closure-related complications through 30 days:
 
 
• Access site-related bleeding requiring greater than 30 minutes to achieve initial arterial hemostasis;
 
• Access site-related hematoma > 6 cm documented by ultrasound;
 
• Late access site-related arterial bleeding requiring intervention (following hospital discharge);
 
• Ipsilateral lower extremity arterial emboli documented by ultrasound/imaging;
 
• Ipsilateral deep vein thrombosis documented by ultrasound;
 
• Access site-related vessel laceration;
 
• Access site wound dehiscence;
 
• Localized access site infection treated with intramuscular or oral antibiotics;
 
• Arteriovenous fistula not requiring treatment, documented by ultrasound/imaging;
 
• Pseudoaneurysm requiring thrombin injection or fibrin adhesive injection;
 
• New onset neuropathy in the ipsilateral lower extremity not requiring surgical repair.
 

Pre-Operative Inclusion Criteria
	
 
1. 18 to 80 years of age;
 
2. Capable and willing to give informed consent;
 
3. Acceptable candidate for an elective, non-emergent ipsilateral peripheral interventional endovascular procedure via antegrade access of the femoral artery using a 5, 6 or 7 Fr introducer sheath;
 
4. Acceptable candidate for post-procedural manual compression;
 
5. Able and willing to complete a follow-up office visit between 1-15 days post-procedure, and subsequent follow-up telephone assessment between 23-37 days;
 
6. Subject is able to ambulate at least 20 feet, with or without assistance (e.g., ambulatory amputee);
 
7. Acceptable candidate for emergent vascular surgery.
 


Pre-Operative Exclusion Criteria
	
Subjects will be excluded from participating in this registry if they meet any of the following criteria prior to initiation of the endovascular procedure:
 
 
1. Advanced refusal of blood transfusion, if necessary;
 
2. Active systemic or cutaneous infection or inflammation;
 
3. Pre-existing immunodeficiency disorder and/or chronic use of systemic steroids;
 
4. Known, significant history of bleeding diathesis, coagulopathy, or current platelet count < 100,000 cells/mm^3, baseline INR ≥1.8, or fibrinogen level less than 150 mg/dl (if received a fibrinolytic agent within prior 24 hours) based on institution's standard pre-operative lab values;
 
5. Severe co-existing morbidities having a life expectancy of less than 90 days;
 
6. Currently involved in any investigational clinical trials that have not completed their primary endpoint and/or may interfere with the conduct of this registry, per Investigator's assessment;
 
7. Previous ipsilateral femoral arteriotomy with any of the following conditions: 
 
a. access within ≤ 10 days
 
b. any residual hematoma, significant bruising, or known associated vascular complications;
 
c. within ≤ 90 days, use of an intra-vascular closure device (i.e., Angioseal);
 
 
 
8. Planned / staged endovascular or surgical procedures within the next 10 days, prior to office visit (excluding planned/anticipated minor amputation);
 
9. Previous vascular grafts or surgery at the target vessel access site;
 
10. Known history of deep vein thrombosis in the ipsilateral limb within the past 30 days, unless confirmed to be resolved by ultrasound prior to enrollment;
 
11. Major amputation (i.e., above the ankle) of the ipsilateral lower extremity is planned/anticipated within next 30 (± 7) days, prior to study exit;
 
12. Large pannus, which may prevent antegrade access without significant tissue displacement, in the opinion of the investigator;
 
13. Significant anemia with a hemoglobin level less than 10 g/dL or
 

--	--

	
a hematocrit less than 30% based on institution's standard pre-operative lab values;
 
14. Renal insufficiency (serum creatinine of > 2.5 mg/dl);
 
15. Females who are pregnant, planning to become pregnant within 3 months of the procedure, or lactating;
 
16. Extreme morbid obesity (BMI greater than 45 kg/m^2) or underweight (BMI less than 20 kg/m^2);
 
17. Known allergy/adverse reaction to bovine derivatives;
 
18. Administration of low molecular weight heparin (LMWH) within 8 hours of the procedure.

Intra-Operative Exclusion Criteria
	
Subjects will be excluded from participating in this registry if any of the following exclusion criteria occur during the endovascular procedure, prior to enrollment (i.e., prior to insertion of VASCADE VCS):
 
 
1. Use of a final introducer sheath > 12 cm (or > 15 cm in overall length), or not 5, 6 or 7 Fr diameter;
 
2. Contralateral femoral arterial access with > 5 Fr catheter that is not successfully closed with a closure device during the index procedure;
 
3. Index groin involves a previously placed permanent closure device (e.g., Starclose), where the device cannot be visualized to confirm that it is at least 1 cm proximal or distal to the puncture site;
 
4. Femoral artery diameter less than 6 mm at access site;
 
5. Angiographic evidence of moderate to severe calcium, > 50% stenosis, or a stent within 1 cm of the puncture site;
 
6. Overlapping Common Femoral Vein and Femoral Artery at access site;
 
7. Presence or placement of ipsilateral venous sheath during procedure;
 
8. Antegrade arterial access site:       
 
a. is a side stick
 
b. is NOT a single anterior wall femoral puncture
 
c. is NOT below the inguinal ligament / lower half of femoral head and not below the inferior epigastric artery origin from the external iliac artery;
 
 
 
9. More than one ipsilateral arterial access site is required in the
 

	
index limb (e.g., femoral or other);
 
10. Intra-procedural bleeding around sheath, or suspected intraluminal thrombus, hematoma, pseudoaneurysm, or AV fistula;
 
11. Evidence of arterial insufficiency, emboli, or new stenosis / occlusion in the ipsilateral limb at the conclusion of the index intervention (i.e., complications occurring from untreated, or suboptimal treatment of disease);
 
12. Systemic hypertension (BP greater than 180/110 mmHg) or hypotension (BP less than 90/60 mmHg) just prior to enrollment;
 
13. Length of the tissue tract, the distance between the anterior arterial wall and skin, is estimated to be less than 2.5 cm;
 
14. If the physician deems that a different method should be used to achieve hemostasis of the arterial site;
 
15. Upon final angio/fluoro assessment of the final introducer sheath to be used for VASCADE delivery, documented evidence of:
 
a. inadequate sheath placement (e.g., location, position, angle), and/or
 
b. any kinking of the procedural sheath prior to enrollment and insertion of the VASCADE VCS.

Study Administration	
Sponsor	Cardiva Medical, Inc. [name]
Clinical CRO & Data Management	Chellex Clinical Outsourcing, LLC [name]
Safety Monitoring	An Independent Physician Adjudicator (IPA) will review and adjudicate all serious device-related adverse event reports, deaths, and all minor and major access site closure-related complications for a determination of both seriousness and closure-relatedness. All adverse events and device failures will be evaluated as complaints and determinations made as to whether the complaint represents an event which is required to be reported to FDA under 21 CFR Part 803, Medical Device Reporting.

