**Table 1. Registry Event Schedule**

	Up to 8 Weeks Before Procedure	Procedure	Post-Procedure/ Hospital Discharge	1-15 Days Post-Procedure	23-37 Days Post-Procedure
Informed Consent 	X				
Demographics/ Medical History / Risk Factors	X				
Index limb assessment 	X		X	X	X
Femoral access site assessment (angiographic)		X	X	X	X
Anticoagulant/antiplatelet regimen 	X	X	X		
Pre-op Inclusion / Exclusion Criteria assessment	X				
Laboratory tests 	X				
Intra-procedural Exclusion Criteria assessment & acknowledgement of intent to enroll		X			
Treated with VASCADE VCS		X			
TTH determination		X			
TTA determination			X		
TTD determination			X		
Procedure Success		X			X
Adverse Events 		X	X	X	X
Office Visit				X	
Telephone follow-up					X

 If informed consent is obtained > 30 days prior to procedure, the subject's verbal re-confirmation of consent should be documented in the medical record prior to the procedure.

 Index limb assessment includes Rutherford Classification, assessment of peripheral pulses, any wounds, amputation history and/or planned amputation, existing neuropathy, and ambulatory status.

 Specific medication regimen within 24 hours prior to enrollment through completion of index procedure.

 For subjects on warfarin, INR should be taken within 24 hours before procedure. "Laboratory tests" refer to exclusion criteria requirements, according to standard of care for these procedures at each site.

 Required adverse event reports: serious, device-related injury or death; minor or major access site closure-related complications; any event that is deemed by Investigator to be clinically significant AND related to the device, the access site or the index limb (See Section 13).

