## 13.3. Registry Reporting Requirements for Adverse Events

The following adverse events must be reported in this post-market registry:

- serious, device-related adverse events (i.e., "reportable")
- major or minor access site closure-related complications (serious and non-serious), as defined in Section 8
- any adverse event that, in the Investigator's opinion, is clinically significant AND is any one of the following:
  - device-related
  - access site-related
  - access limb-related.

1. Complete an Adverse Event eCRF within 24 hours of knowledge of a reportable event. Medical records (e.g., procedure notes, operative notes, discharge summary, relevant progress notes, imaging or lab studies) may be requested by Cardiva Medical or its designee for event review and potential adjudication.

2. For questions, contact [name] at [contact].

All required adverse events (AE) (serious and non-serious) will be recorded on the eCRF and monitored from the time of enrollment through study exit.

In addition to 21 CFR 803 seriousness definitions, the following definitions for Serious Adverse Events will be used for consistency with published comparative data (per GCP, E6).

A serious adverse event (SAE) is defined as an event which leads to:

- Death due to any cause
- Life-threatening condition
- Results in persistent or significant disability/incapacity
- Requires in-patient hospitalization or prolonged hospitalization
- Necessitates an intervention to prevent a permanent impairment of a body function or permanent damage to a body structure
- Results in congenital abnormality

The following definitions for rating severity of adverse events will be used:

- Mild: Awareness of signs or symptoms, but easily tolerated; are of minor irritant type; causing no loss of time from normal activities; symptoms would not require medication or a medical evaluation; signs or symptoms are transient.
- Moderate: Interferes with the subject's usual activity and/or requires symptomatic treatment.
- Severe: Symptom(s) causing severe discomfort and significant impact of the subject's usual activity and requires treatment.

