**INDEPENDENT PHYSICIAN ADJUDICATOR (IPA)**

An independent physician, qualified by training and experience in the field of interventional cardiology or radiology, who will review and adjudicate all reported adverse events that are both serious and device-related; and all reported major and minor access site closure-related complications. The IPA is not a participant in the trial and is independent of Cardiva Medical.

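### Which events reach the adjudicator depends mainly on the site's own relatedness label, so non-fatal access-site and limb events that the site attributes elsewhere have no required review

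*Combined protocol and SAP*

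**What the plan says.** The Safety Monitoring row of the synopsis states: "An Independent Physician Adjudicator (IPA) will review and adjudicate all serious device-related adverse event reports, deaths, and all minor and major access site closure-related complications", and gives the purpose as "for a determination of both seriousness and closure-relatedness". Deaths appear there with no relatedness condition.

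The definition of the adjudicator in Section 18.2 describes a physician "who will review and adjudicate all reported adverse events that are both serious and device-related; and all reported major and minor access site closure-related complications". Deaths are not listed separately.

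The reporting duty is wider. Besides serious device-related events and the complications of Section 8, Section 13.3 requires "any adverse event that, in the Investigator's opinion, is clinically significant AND is any one of the following": device-related, access site-related or access limb-related. Footnote 5 of Table 1 has the same scope: "any event that is deemed by Investigator to be clinically significant AND related to the device, the access site or the index limb". For reportable events, Section 13.3 says that medical records may be requested "for event review and potential adjudication". It does not say when that happens or who decides.

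Sections 8.3 and 9.2.3.1 define the primary complication outcome as the 30-day proportion of subjects with any major closure-related complication, reported with a 95% Wilson interval. Section 9.2.3.2 does the same for minor complications. Neither section says whether the site's classification or the adjudicator's is counted.

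**The concern.** The adjudicator is there to decide closure-relatedness, yet most events reach the adjudicator only after the site has made a relatedness judgement of its own. If a site wrongly calls an event closure-related, the adjudicator sees it. If a site wrongly calls a non-fatal event unrelated to the device and the closure, nothing requires that anyone independent sees it.

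This matters because attribution is hard in this registry. Every subject has an ipsilateral peripheral intervention through the same access, and Section 9.2.1 describes a critical limb ischemia population. New ischemia or neuropathy after the procedure may come from the disease, the intervention or the closure. The composite that depends on this judgement is the primary complication outcome, and it also enters Procedure Success (Section 8.2). With a single arm, no control group is subject to the same under-attribution.

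**Working it through.** The plan gives no figure that depends on this point, and Section 9.3 sets the sample size by judgement, so there is nothing to reproduce. The check traces the route of events and then shows the scale.

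**Step 1: routes to the adjudicator.**

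| Event | Must be reported? | Required adjudication? |
|---|---|---|
| Filed by the site as a major or minor closure-related complication | Yes (13.3) | Yes (synopsis and 18.2) |
| Serious and called device-related by the site | Yes (13.3) | Yes (synopsis and 18.2) |
| Death not called device-related or closure-related | Not named in the required list of 13.3, though its SAE definition includes death from any cause | Yes in the synopsis; not in 18.2 |
| Non-fatal, clinically significant, access-site- or limb-related, but neither of the first two rows | Yes (13.3, Table 1 footnote 5) | No; possible only, without a trigger |

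The last row is the gap.

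**Step 2: which components can fall into the gap.**

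- Neuropathy and nerve injury: the Section 18.2 definitions (surgical repair, no surgical repair, and permanent injury) all require a closure-related nerve injury. A site that judges a neuropathy unrelated will, by definition, not file it.
- Limb-threatening ischemia: neither the item in 8.3 nor its definition in 18.2 mentions relatedness, so a site could file it on clinical grounds. The composite it belongs to is nevertheless called closure-related, so a site that blames underlying disease could leave it out.
- Bleeding requiring transfusion: defined in 18.2 by its origin at the index arteriotomy. This leaves little room for attribution, so the concern is weak here.

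**Step 3: what one patient is worth.** Inputs: n = 100 (Section 4.2, the maximum) and z = 1.96. The Wilson limits are [p + z²/(2n) ± z√(p(1−p)/n + z²/(4n²))] / (1 + z²/n).

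- 0/100: 0% (0 to 3.7%)
- 1/100: 1% (0.2 to 5.4%)
- 2/100: 2% (0.6 to 7.0%)
- 3/100: 3% (1.0 to 8.5%)

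Each added patient moves the estimate by 1/100, or 1 percentage point. A missed major complication also raises Procedure Success by 1 point if that subject had Device Success.

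**Step 4: how often, under assumptions.** The documents give neither the true rate nor the share of events that sites would under-attribute. Assume a true major rate p and a share s labelled unrelated and not forwarded. The chance that at least one event is never reviewed is 1 − (1 − ps)^100, and the expected observed rate is p(1 − s).

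- p = 1%, s = 10%: 1 − 0.999^100 = about 10%; expected rate 0.9%
- p = 2%, s = 25%: 1 − 0.995^100 = 39%; expected rate 1.5%
- p = 5%, s = 50%: 1 − 0.975^100 = 92%; expected rate 2.5%

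A range this wide shows only that the effect could be negligible or material. It does not estimate the effect.

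**The case against.** A reader might infer that the adjudicator sees only events already labelled related, and so can remove events from the primary rate but never add them. The documents do not support that.

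- The synopsis sends deaths regardless of relatedness.
- Serious device-related events form a category separate from closure-related complications. Such an event, or a death, that the site did not file as closure-related can still be found closure-related. That is a route upward.
- Section 13.3 leaves adjudication open for other reportable events, so recovery is possible, though not assured.
- Removal is not established either. Sections 8.3 and 9.2.3 never say that the adjudicator's decision overrides the site's. If the site's classification is what is counted, adjudication changes nothing in either direction.

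It can also be argued that Section 13.3 asks for complications as Section 8 defines them, and that several items there carry no relatedness wording, so sites may file on clinical criteria and leave causation to the adjudicator. That stands for some items, notably bleeding, and in part for ischemia. It does not stand for neuropathy. Source verification (Section 11.1) gives some further protection, but it is not adjudication.

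Finally, the study is descriptive, with no test or margin, so no formal decision turns on a shift of one event, and taking out truly over-attributed events is correction rather than bias. Both statements are right. They limit the consequence; they do not supply the missing route for under-attributed events.

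**Conclusion.** The point holds in this form: required review depends mainly on the site's relatedness label, and a non-fatal, reportable access-site or limb event that the site calls neither serious and device-related nor a closure-related complication has no required route to the person who decides closure-relatedness. Separately, the synopsis and Section 18.2 disagree on deaths.

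The asymmetry can bias the major and minor rates downward and Procedure Success upward. That direction rests on three assumptions: sites under-attribute at least some events, the adjudicator would correct them, and the adjudicated classification is the one analysed. If the site's classification is analysed instead, under-attributed events stay missing and over-attributed ones stay in, so the net direction is unknown.

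The size is 1 percentage point per patient at n = 100. The frequency cannot be obtained from the documents. This is a gap worth closing because closing it is cheap; it does not show that the registry's rates will be wrong.

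**What to change.** 1. In the synopsis and in the Section 18.2 definition, send the adjudicator all deaths and every event reported under 13.3 that is device-, access-site- or index-limb-related, whatever the site's view on closure. Replace the open-ended wording on possible adjudication in 13.3 accordingly.
2. Reconcile the synopsis and 18.2 on deaths, and name deaths in the required list of 13.3 so that they arrive.
3. State in Section 9.2.3 that the adjudicated classification defines the major and minor complication rates, and that Procedure Success follows from it. Without this, wider routing need not change any reported figure.
4. Report the number of events reclassified in each direction.

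The cost is protocol wording and modestly more work for the same adjudicator. Sites already have to enter the access-site, limb and device events on the adverse event eCRF. Naming deaths in 13.3 may add an occasional report.
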